#### 14.3.5. End of Study Visit

NOTE: Subjects will complete an End of Study Visit 4 weeks following their last study visit. For subjects who have already completed Visit 36 (Week 384) or beyond, an End of Study Visit should be completed 4 weeks after their next visit (scheduled or unscheduled). For subjects who complete a Premature Study Treatment Withdrawal Visit, this will also be used as the End of Study Visit.

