2.2 Overall Study Duration and Follow-Up

Eligible subjects were enrolled at Week 96 (Visit 24) of their previous BG00012 study (109MS301 or 109MS302), which would serve as the Baseline Visit for this extension study. If the Baseline Visit could not be combined with Visit 24 of their previous BG00012 study, the subjects may have been randomized within 6 months of Visit 24, provided that they still were eligible for enrollment. The Baseline visit assessments may have been repeated if there was a gap in study treatment.

Subjects reported to the study site every 4 weeks for the first 24 weeks (Visit 1 through Visit 6) and every 12 weeks thereafter for up to 8 years.

Subjects who completed the Week 384 visit (Visit 36), regardless of further need to monitor lymphocytes on study, completed an End of Study Visit at Week 388 ± 7 days. For subjects who have completed Visit 36, an End of Study Visit was completed 4 weeks after their next visit (scheduled or unscheduled), regardless of further need to monitor lymphocytes on study. Subjects who permanently discontinued BG00012 prior to Week 384, regardless of further need to monitor lymphocytes on study, completed a Premature Study Treatment Withdrawal Visit within 4 weeks after their last dose of BG00012. Subjects who completed BG00012 treatment or permanently discontinued BG00012 for any reason and who had a lymphocyte count <LLN were not withdrawn from the study. These subjects were followed according to Protocol Section 11.3.

For subjects who have already completed Visit 36 (or beyond) prior to the Protocol Version 8, an End of Study Visit was completed 4 weeks after their next visit (scheduled or unscheduled), regardless of further need to monitor lymphocytes on study. For subjects who have not completed Visit 36 prior to Protocol Version 8, Visit 36 served as the last scheduled Visit and an End of Study Visit was completed 4 weeks after their next visit (scheduled or unscheduled), regardless of further need to monitor lymphocytes on study.

Premature Study Withdrawal Visits and Unscheduled Relapse Assessment Visits were performed as necessary. All efforts were made to keep the subjects' visit schedule relative to their Baseline Visit (Day 1). All subjects who discontinued the study treatment were considered to be prematurely withdrawn from the study.

The end of study is defined as the Last Patient, Last Visit for final collection of data for the primary outcome

2.3 **MRI**

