3.6 Study Activities 109MS303 (Unscheduled and Post-Treatment Visits)

Tests and Assessments	End of Study Visit ¹	Unscheduled Relapse Assessment Visit ²	Premature Study Treatment Withdrawal Visit ³	Lymphocyte Follow-Up (Up to 96 Weeks After Last Dose) ⁴
Physical Examination		X	X	
Vital Signs	X	X	X	X
Hematology	X^3	X	X^3	X
Blood Chemistry	X	X	X	
Urine Pregnancy Test ⁵	X	X	X	
Urinalysis	X^6	X^6	X^6	
Brain MRI ⁷ Scan ± Gd ⁸	Schedu	aled MRI scans were performed i	in protocol versions 1 through	6.
EDSS		X	X	
Visual Function Test		X	X	
SF-36 and EQ-5D		X	X	
Relapse Assessment		X		
Concomitant Therapy and Procedures Recording	N	Monitor and record throughout th	e study as per Protocol Section	n 11.6
AE/SAE Reporting		Monitor and record throughout the	he study as per Protocol Section	on 15

AE = adverse event; EDSS = Expanded Disability Status Scale; EQ-5D = EuroQol EQ-5D Health Survey; Gd = gadolinium; LLN = lower limit of normal; MRI = magnetic resonance imaging; SAE = serious adverse event; SF-36 = Short-form 36 Health

Survey

- 1. For subjects who have already completed Visit 36 or beyond, an End of Study Visit should be completed 4 weeks after their next visit (scheduled or unscheduled).
- 2. Unscheduled Relapse Assessment Visit is to be carried out within 5 days of suspected relapse.
- 3. Subjects who permanently discontinue BG00012 prior to Week 384 (Visit 36) should complete a Premature Study Treatment Withdrawal Visit within 4 weeks of their last dose. The Premature Study Treatment Withdrawal Visit will serve as the End of Study Visit.
- 4. Lymphocyte follow-up as per Protocol Section 11.3.
- 5. For women of childbearing potential.
- 6. If urinalysis is abnormal, see Protocol Section 11.2.
- 7. Only in subjects who had MRI scans as part of Studies 109MS301 and 109MS302 and in 109MS303 up through and including Amendment 6.
- 8. MRI must not be performed within 30 days of receiving a course of steroid.

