6.5.6 Analysis of Absolute Lymphocyte Counts

Subjects who temporarily withhold, or permanently discontinue study treatment for any reason and have a lymphocyte count <LLN will continue protocol-required visits and assessments and will also be followed up every 4 weeks for 24 weeks, then every 12 weeks (unless clinically indicated more often or at the Investigator's discretion) until the lymphocyte count is ≥LLN or for up to 48 weeks following drug discontinuation, whichever occurs sooner.

In general, the lymphocyte follow-up analysis may include subjects who have at least one ALC < LLN during the treatment period or at the treatment discontinuation and have at least one ALC value during the lymphocyte follow-up period. Patients who have any post lymphocyte follow-up baseline values may be included in the follow-up analysis. ALCs collected during the lymphocyte follow-up period will be analyzed.

The lymphocyte follow-up period is defined as the time starting from the date of temporary dose interruption or study drug discontinuation. The start date of the lymphocyte follow-up period is defined as the start date of temporary dose interruption or the treatment end date. The last observed value collected on or prior to the date of temporary dose interruption or study drug discontinuation will be the reference point (lymphocyte follow-up baseline). Data that are collected during the lymphocyte follow-up period will be assigned to an appropriate visit by using the mid-point of the two visits windowing scheme. Visits will be mapped every 4 weeks for 24 weeks and then every 12 weeks afterward.

The by-visit summary of actual value change and percent change from BG00012 baseline and the lymphocyte follow-up baseline in ALC during the lymphocyte follow-up period will be presented. The by-visit summary of actual value change and percent change from the study baseline in ALC during the whole study period will also be presented. In addition, graphical display of median (Q1/Q3) of actual value in ALC in the whole study period will be presented; graphical display of median (Q1/Q3) of percent change from BG00012 baseline and lymphocyte follow-up baseline will be presented.

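### By-visit ALC summaries after stopping drug depend on who is still being tested, so later medians do not describe recovery in the whole group

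*SAP*

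**What the plan says.** **The summary.** SAP 6.5.6 plans "The by-visit summary of actual value change and percent change from BG00012 baseline and the lymphocyte follow-up baseline in ALC" during lymphocyte follow-up, plus graphs of medians and quartiles. I read the sentence as covering actual value, change and percent change. Only collected ALCs enter, and SAP 6.1 rules out imputation in general.

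**When testing stops.** SAP 6.5.6 follows subjects below LLN until they reach LLN "or for up to 48 weeks following drug discontinuation, whichever occurs sooner". Protocol 11.3 and Table 3 also stop at LLN, with limits of 48 or 96 weeks.

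**Whether other visits continue.** The documents point both ways.
- SAP 6.5.6 says that those who withhold or permanently discontinue "will continue protocol-required visits and assessments and will also be followed up every 4 weeks for 24 weeks, then every 12 weeks". SAP 2.2 says that subjects who completed or permanently discontinued "for any reason and who had a lymphocyte count <LLN were not withdrawn from the study".
- SAP 2.2 also says: "All subjects who discontinued the study treatment were considered to be prematurely withdrawn from the study". Protocol 14.3.5 says: "For subjects who complete a Premature Study Treatment Withdrawal Visit, this will also be used as the End of Study Visit". SAP 3.6 agrees: "The Premature Study Treatment Withdrawal Visit will serve as the End of Study Visit".

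**The analysis period.** SAP 6.5.6 says: "The lymphocyte follow-up period is defined as the time starting from the date of temporary dose interruption or study drug discontinuation". It gives no end.

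**The concern.** A by-visit summary of observed values describes a group only if presence at a visit is unrelated to the outcome. Here a subject who reaches LLN may have no later test because LLN was reached. The recovery value counts at its own visit, and then the subject is gone. Later visits hold those who have not recovered, plus whoever is tested for another reason.

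What is at stake is the use of the display. The amendment rationale for Protocol 11.3 says follow-up was lengthened as a safety measure, because full recovery may take more than 6 months after stopping. A later median over a changing set of subjects answers that question poorly. The open-ended follow-up period adds a second problem: Table 3 lets some withheld subjects restart BG00012, and nothing in SAP 6.5.6 keeps their on-drug values out of a post-drug summary.

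**Working it through.** The plan gives no figure on this point, so there is none to reproduce. The check has two parts: the text, and simulations that show direction and sensitivity.

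**1. Who has a scheduled ALC after reaching LLN (current protocol)**

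| Group | Tests after LLN | Source |
|---|---|---|
| Permanent discontinuers | None; the withdrawal visit is the End of Study Visit, and only Lymphocyte Follow-Up comes after it | Protocol 4.6, 14.3.5, 14.3.8 |
| Completers of Visit 36 | None after the End of Study Visit (Week 388) | Protocol 7.2.3, 4.6 |
| Temporarily withheld | Scheduled tests go on | Protocol 11.2.1 |

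SAP 6.5.6 does not separate these groups.

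**2. What is compared.** Let T be the first visit with ALC at or above LLN. The observed median at visit v uses subjects with T ≥ v, plus the share still tested after recovery. The target is the median over all subjects at v.

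**3. Actual ALC, Week 48 median per mm³.** Assumptions, none from the documents: LLN 910, mean pre-treatment ALC 1900, ALC at stopping about 35% of that, base half-time 16 weeks with 80% of the loss regained, 15% noise, 200,000 subjects per run, unrecovered subjects never lost.

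| Setting | All | Observed |
|---|---|---|
| Base, 4-weekly to Week 24, none retested | 1297 | 801 |
| 12-weekly tests | 1296 | 823 |
| First 24 weeks of tests fixed | 1296 | 829 |
| Half-time 8 weeks | 1403 | 803 |
| Half-time 32 weeks | 1124 | 775 |
| 30% of the loss regained | 839 | 655 |
| 30% retested after recovery | 1298 | 1141 |
| 60% retested | 1293 | 1247 |
| All retested | 1296 | 1296 |

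The base gap is 1297 − 801 = 496. It falls to 1298 − 1141 = 157 with 30% retested, 1293 − 1247 = 46 with 60%, and 0 with all. Across half-times of 8 to 32 weeks the all-subject median moves by 1403 − 1124 = 279, but the observed median by only 803 − 775 = 28.

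**4. Percent change from follow-up baseline, Week 48.** A second assumed model has LLN 0.91 × 10⁹/L, ALC at stopping uniform from 0.40 to 0.90, an exponential rise to a target with mean 1.6 and SD 0.35, half-time log-SD 0.8, 10% noise and 12-weekly tests. For half-times of 12/24/48 weeks:
- All subjects: +125/+99/+68%.
- None retested: +54/+55/+46%, so gaps of 71/44/22 points.
- 50% retested: +120/+92/+62%, so gaps of about 5 to 7 points.

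**5. The sign can reverse for percent change.** With none retested, target SD 0.1, half-time log-SD 0.3 and half-time 24 weeks, the result is +39.9% for all against +49.3% observed (target mean 1.0), and +73.9% against +93.0% (target mean 1.3). In the step 3 model, when subjects differ mainly in depth of nadir, percent change is +185% for all against +220% observed. In that same run actual ALC is 1343 against 856. Those who remain have deeper nadirs, so their denominators are small.

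**6. Loss of unrecovered subjects pushes the other way.** In the step 4 model (half-time 24 weeks, half of recovered subjects retested), losing 20% of unrecovered subjects per visit gives +99.0% for all against +99.2% observed. At 30% loss the observed figure is +102.5%.

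**7. A measure that does not depend on retesting.** In the step 4 model the proportion with a first ALC at or above LLN by Week 48 is 97/92/80% for the three half-times (65/57/45% with target mean 1.0), whatever share is retested afterwards.

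**8. Follow-up schedules side by side**

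| Source | Who | Schedule | Limit after stopping |
|---|---|---|---|
| SAP 6.5.6 | Withheld or permanently discontinued; completers not named | 4-weekly for 24 weeks, then 12-weekly | 48 weeks |
| Protocol 11.3 | Completers and discontinuers outside Table 3 | 12-weekly | 48 weeks |
| Table 3, first limb | Met the Temporary Withholding Rule | 4-weekly for 24 weeks, then 12-weekly | 96 weeks |
| Table 3, second limb | As above, at end of study and below LLN | 12-weekly | 48 weeks |

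If Protocol 11.3 is followed, Weeks 8, 16 and 20 on the SAP grid would come mainly from Table 3 subjects.

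**The case against.** The case against a serious reading is good, and most of it stands as a limit.

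- **Continued visits.** SAP 6.5.6 says subjects go on with protocol visits, and withheld subjects clearly do. If most are retested, the effect is small (steps 3 and 4). A reader might infer that everyone leaves at LLN; the documents do not support that.
- **Direction.** A reader might infer that the display always makes recovery look worse and so errs on the safe side. Steps 5 and 6 show otherwise: percent change from follow-up baseline can be too favourable, and loss of unrecovered subjects can cancel or reverse the gap.
- **Timing.** Table 3 and SAP 6.5.6 can be read as fixing the first 24 weeks of tests, with the stop at LLN governing only the later phase. Depletion would then start only after Week 24.
- **Text not visible.** The SAP text between 6.5.6 and 6.5.8, the exploratory objectives and part of the lymphocyte sentence in Protocol 16.4.2 cannot be seen. A reader might infer that no time-to-recovery analysis is planned; that cannot be said.
- **Scope.** Protocol 16.4.2 promises a descriptive summary, no visible objective names time to recovery, and SAP 6 already gives the number with data.

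None of this removes the core: unless retesting is complete, who contributes late depends on recovery, and the visible text neither separates the groups nor ends the follow-up period. The schedule mismatch is documentary; it adds no weight to the bias argument.

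**Conclusion.** The point holds as a minor improvement to a descriptive safety display. Later by-visit medians in SAP 6.5.6 do not describe how fast or how fully the whole group recovers, because dedicated testing ends at LLN and two of the three groups have no other scheduled ALC after their End of Study Visit.

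The direction is firm only for actual ALC, and only if unrecovered subjects stay in follow-up: later medians are then too low. For percent change from follow-up baseline the error can go either way. The size is unknown. LLN, recovery speed, extent of recovery, loss to follow-up and the share retested are all assumed here; under those assumptions the Week 48 gap in median ALC runs from none (all retested) to several hundred per mm³ (none retested). The missing end of the follow-up period and the conflicting schedules rest on the text alone.

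**What to change.** In SAP 6.5.6:
1. End the follow-up period for analysis at restart of BG00012, so that on-drug values are not counted as post-drug.
2. Unless the text not visible already has it, add a cumulative incidence estimate of time from last dose, or from start of withholding, to first ALC at or above LLN. Include only subjects below LLN at follow-up baseline, since the section also admits subjects with one earlier low value. Censor at the last ALC. Treat restart and start of alternative MS therapy as competing events, because restart itself follows a rise in counts. Show permanent discontinuers and completers apart from withheld subjects.
3. Keep the by-visit tables as supportive, with the cumulative number recovered beside the number with data.

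Reconcile the schedule and duration in SAP 6.5.6, including completers, with Protocol 11.3 and both limbs of Table 3. Reconcile the SAP 2.2 and 6.5.6 wording on continued visits with Protocol 14.3.5. Which schedule applies is for the sponsor to settle.

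The cost is a revision of SAP 6.5.6, one extra table and one figure. No new data are needed.

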**Now reads:**

Tests and Assessments	Subjects with lymphocyte count $\geq$ LLN	Subjects with lymphocyte count $<$ LLN to $\geq 500/\text{mm}^3$	Subjects with lymphocyte count $< 500/\text{mm}^3$
Hematology	Every 24 weeks	Every 12 weeks	Every 4 weeks

[REDACTED]

**Rationale:** The table has been added to provide guidance on the frequency of collection of blood samples for hematology and additional exploratory analyses.

CONFIDENTIAL

The information contained herein may not be used, disclosed, or published without the written consent of Biogen Idec MA Inc.

Section 6.2, Additional Objectives

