## PRIMARY REASON FOR AMENDMENT

The primary reason for this amendment to Protocol 109MS303 is to update the safety reporting information.

New text is shown in **bold** type; deleted text is shown with a ~~strikethrough~~.

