### Section 4.3

**Change:** The frequency of some study procedures (clinical chemistry, hematology, urinalysis, physical examination, and urine pregnancy testing) was decreased from every 12 weeks to every 24 weeks during Year 4 through 8 of the treatment period. The study activities chart (Chart 2 of 2) was revised and new study activities charts for Years 2 and 3, Years 4 through 8, and post-treatment and unscheduled visits were created to reflect the new schedule of assessments as well as the extended duration of the study.

CONFIDENTIAL

The information contained herein may not be used, disclosed, or published without the written consent of Biogen Idec MA Inc.

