### 4.3 Study Activities (Years 4 Through 8 Treatment Visits Effective with Protocol Version 3)

Year	Year 4				Year 5				Year 6				Year 7				Year 8			
Visit	17	18	19	20	21	22	23	24	25	26	27	28	29	30	31	32	33	34	35	36
Study Week (±7 days)	156	168	180	192	204	216	228	240	252	264	276	288	300	312	324	336	348	360	372	384
Tests and Assessments 																				
Physical Examination		X		X		X		X		X		X		X		X		X		X
Vital Signs	X	X	X	X	X	X	X	X	X	X	X	X	X	X	X	X	X	X	X	X
Hematology		X		X		X		X		X		X		X		X		X		X
Blood Chemistry		X		X		X		X		X		X		X		X		X		X
Urine Pregnancy Test 		X		X		X		X		X		X		X		X		X		X
Urinalysis		X 		X 		X 		X 		X 		X 		X 		X 		X 		X 
Brain MRI  Scan ± Gd				X 				X 				X 				X 				X 
EDSS		X		X		X		X		X		X		X		X		X		X
Visual Function Test		X		X		X		X		X		X		X		X		X		X
SF-36 and EQ-5D				X				X				X				X				X
Dispense Study Treatment 	X	X	X	X	X	X	X	X	X	X	X	X	X	X	X	X	X	X	X	
Concomitant Therapy and Procedures Recording	Monitor and record throughout the study as per Section 11.5																			
AE/SAE Reporting	Monitor and record throughout the study as per Section 15																			

1. Tests and assessments must be completed prior to study treatment distribution.
2. For women of childbearing potential. Results must be known prior to study treatment distribution.
3. Urine cytology must be performed if subject experiences hematuria (of unknown etiology) on 2 consecutive tests. If urine cytology is positive during the treatment period, subject must permanently discontinue study treatment (see Section 11.3).
4. Only in subjects who had MRI scans as part of Studies 109MS301 and 109MS302.
5. MRI must not be performed within 30 days of receiving a course of steroids.
6. The date and Study Visit/Week at which subjects are switched to open-label treatment should be recorded on the dosing CRF.

CONFIDENTIAL

The information contained herein may not be used, disclosed, or published without the written consent of Biogen Idec MA Inc.

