6.5.4 Analysis of Clinical Laboratory Data

The following clinical laboratory parameters are assessed in the protocol:

- Hematology: hemoglobin, hematocrit, red blood cell count, WBC count (with differential) and platelet count.
- Blood chemistry: sodium, potassium, chloride, total bilirubin, alkaline phosphatase, alanine transaminase/serum glutamate-pyruvate transaminase (ALT/SGPT), aspartate transaminase/serum glutamic-oxaloacetic transaminase (AST/SGOT), lactate dehydrogenase, gamma-glutamyl-transferase (GGT), blood urea nitrogen (BUN), creatinine, bicarbonate, calcium, magnesium, phosphate, uric acid, and glucose.
- Urinalysis: color, specific gravity, pH, protein, glucose, blood, ketones, microscopy, β₂-microglobulin, and microalbumin.
- Urine cytology

Analyses for laboratory data involving baseline value will be based on BG00012 Treatment Baseline (as defined above in Section 6.3.1).

Shift analyses

Laboratory data will be summarized using shift tables where appropriate. Each subject's hematology and blood chemistry values will be flagged as "low", "normal", or "high" relative to the normal ranges of the central laboratory, or as "unknown" if no result is available. Each subject's urinalysis values will be flagged as "positive", "negative", or if no value is available, "unknown".

Shifts from baseline to high/low status for hematology and blood chemistry parameters and shifts from baseline to high/positive status for urinalysis will be presented. Subjects need to have at least one post-baseline evaluation in order to be included in the analysis. In addition, shifts from baseline to the worst post-baseline value will be presented for relevant laboratory tests by treatment group by clinically relevant categories (e.g., \leq ULN, \geq 1 - \leq 3 xULN, \geq 5 - 10 xULN, \geq 10 - 20 x ULN, \geq 20 x ULN, etc.).

For urine cytology tests results, the number and percentage of subjects with an abnormal post-baseline result will be summarized by treatment group.

Summary of laboratory values over time and other analyses

In addition to the shift analyses, summary of actual values, change from baseline values, and percentage change from baseline values will be presented by visit for quantitative laboratory parameters. Graphs showing mean actual values or mean change from baseline values over time may be presented as well.

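### Odd-numbered Year 4-8 visits reached under Protocol Version 5 had scheduled haematology only for subjects below LLN, so the whole-study by-visit ALC tables and median plot may be biased downward there

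*SAP*

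**What the plan says.** SAP 6.5.6 plans two whole-study ALC displays: "The by-visit summary of actual value change and percent change from the study baseline in ALC during the whole study period will also be presented", and a "graphical display of median (Q1/Q3) of actual value in ALC in the whole study period will be presented". SAP 6.5.4 adds, for laboratory data in general, that a "summary of actual values, change from baseline values, and percentage change from baseline values will be presented by visit for quantitative laboratory parameters". SAP 6.1 bases analyses on observed data without imputation. SAP 6.3.8 assigns each value to a visit window that ends midway between scheduled visits, so each 12-weekly visit has its own timepoint. SAP Section 3 shows only the current schedule. No passage restricts, stratifies or footnotes these displays by protocol version.

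The amendment summaries at the end of the protocol show how haematology was scheduled when the data were collected:

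- **Version 2.** The chart reproduced in the Version 3 amendment marks haematology at every 12-weekly visit, and it ends at Visit 24.
- **Version 3.** The frequency "was decreased from every 12 weeks to every 24 weeks during Year 4 through 8 of the treatment period". The grid headed "Study Activities (Years 4 Through 8 Treatment Visits Effective with Protocol Version 3" marks haematology at even-numbered visits only.
- **Version 4.** The stated purpose of this amendment "is to update the safety reporting information", and its summary shows no haematology change.
- **Version 5.** The added haematology table (then Section 4.4) gives "Every 24 weeks" for subjects at or above LLN, a 12-week interval from below LLN down to 500/mm³, and a 4-week interval below 500/mm³.
- **Version 8 (current).** Protocol 4.5 gives a 12-week interval for subjects at or above LLN. Protocol 14.3.3.1 lists a haematology draw at Visits 17, 19, ..., 35 with no limit by lymphocyte count.

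**The concern.** Under Version 5, whether a scheduled value exists at an odd visit depends on the variable being summarised. Subjects at or above LLN have no scheduled draw there, and subjects below LLN do. A median of observed values then describes a group selected for low counts, and a larger sample does not cure that.

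Long-term safety is the primary objective, and the Version 5 amendment was prompted by PML arising in severe, prolonged lymphopenia. A curve that dips or zig-zags at alternate visits could be read as a drug effect when it reflects who was sampled. A reader of the SAP alone would see only the current schedule and would assume that everyone was tested at each visit.

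**Working it through.** **1. Who had scheduled haematology in Years 4-8**

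| Version | Odd visits (17, 19, ..., 35; Weeks 156, 180, ..., 372) | Even visits (18, 20, ..., 36; Weeks 168, 192, ..., 384) |
|---|---|---|
| 2 | everyone (chart covers Visits 17-23 only) | everyone (to Visit 24) |
| 3 and 4 | no one | everyone |
| 5 | only subjects below LLN | everyone |
| 8 (current) | everyone | everyone |

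Versions 6 and 7 are left out. Their amendment summaries do not print the interval for subjects at or above LLN.

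Only the Version 5 rule selects on ALC. A version that tests everyone adds no bias. A version that tests no one lowers the number of values, but it also contributes nothing to dilute the Version 5 values.

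**2. Which visits could be affected**

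The Version 6 rationale describes about 1000 ongoing patients with more than 4 years of follow-up, and up to 6 years for those treated continuously. Six years less 2 parent-study years is about 4 extension years. The Version 7 rationale gives a median of about 5 extension years. If 12-weekly testing for all returned with Version 6, the affected odd visits lie at roughly Years 4-6, and those in Years 7-8 should be largely free of the effect. The haematology section is listed as affected in both the Version 6 and the Version 8 summaries, so the version that restored 12-weekly testing is not established. If it came after Version 6, more visits are involved.

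**3. Size**

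The plan gives no figure to reproduce. The documents give neither the share of subjects below LLN, nor the spread of ALC, nor the version mix at each visit. All three are assumed below.

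- p = share of subjects below LLN
- r = subjects at the odd visit under Version 5, divided by subjects there under a version that tests everyone (Version 3-4 subjects contribute no scheduled value)
- σ = SD of log ALC, taken as lognormal
- the Version 5 testing class is taken to equal the subject's current state

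For each all-tested subject, Version 5 adds r·p values, all below LLN. Let F be the quantile of the full ALC distribution at which the pooled median sits.

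- Median at or above LLN: F + r·p = 0.5(1 + r·p), so F = 0.5(1 − r·p). This applies when F ≥ p.
- Otherwise: F(1 + r) = 0.5(1 + r·p), so F = 0.5(1 + r·p)/(1 + r).
- Fall in the median = 1 − exp(σ·z(F)), where z is the standard normal quantile.

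Example with p = 0.30, r = 1, σ = 0.40: F = 0.5(1 − 0.30) = 0.35, z = −0.385, exp(−0.154) = 0.857, a fall of 14%. A simulation of this case also put the median at the 35th percentile. With LLN assumed at 0.91 × 10⁹/L, the median moves from 1.12 to 0.96.

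Results with σ = 0.40:

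| Version 5 : all-tested subjects | p = 0.20 | p = 0.30 | p = 0.40 |
|---|---|---|---|
| 25:75 (r = 1/3) | F = 0.467, −3% | F = 0.450, −5% | F = 0.433, −7% |
| 50:50 (r = 1) | F = 0.400, −10% | F = 0.350, −14% | F = 0.350, −14% |
| 75:25 (r = 3) | F = 0.200, −29% | F = 0.238, −25% | F = 0.275, −21% |

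Over a wider grid (p from 0.1 to 0.4, σ of 0.30 and 0.45), the fall runs from 0.4-2.2% at r = 0.1, through 3.7-15.9% at r = 1, to about 22-52% at a visit holding Version 5 values only.

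**4. Relaxing the last assumption**

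A subject's testing class is set by an earlier count, so some Version 5 odd-visit values will be at or above LLN. With correlation ρ between the classifying and the current log ALC (p = 0.30, σ = 0.40):

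| Version 5 : all-tested subjects | ρ = 1.0 | ρ = 0.8 | ρ = 0.6 |
|---|---|---|---|
| 50:50 | −14% | −9% | −7% |
| 25:75 | −5% | −4% | −3% |

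The figures in step 3 are therefore upper bounds within each scenario.

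**5. After the change**

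At even visits, or with Version 5 odd-visit values removed, r = 0 and F = 0.50. No dip from the schedule remains.

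**The case against.** The strongest reply is that the effect may be small and local. The version mix at each visit sets its size and cannot be derived. The figures assume the worst case for testing class. The displays are descriptive, and SAP Section 6 reports the number of subjects with data, so a drop at odd visits would show in the tables. All of this stands. It limits the size and the certainty, but a lower count does not tell the reader that the remaining subjects were selected for low values.

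One could also say that superseded schedule text is no error in the plan. That is true, but the amendment history is used here only as evidence of how the data were collected, and the final analysis generally includes all available data in the locked database.

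Four stronger readings are tempting, and the documents do not support them:

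- **Every odd visit in Years 4-8 will dip.** Only Version 5 selects on ALC, and later odd visits may be unaffected.
- **Version 6 restored testing for everyone.** This is a plausible inference, but no summary states it.
- **Most subjects passed through Version 5 at these visits.** No version dates or counts by visit are given.
- **The share below LLN will be overstated by visit.** No by-visit table of that share is specified.

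Other displays are not affected in this way. The lymphocyte follow-up displays run on time since interruption or discontinuation, and the shift and worst-value tables do not use by-visit medians. No bias is shown for haemoglobin or platelets.

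**Conclusion.** The point holds as a risk confined to part of the ALC display. If the SAP is followed as written, values selected on the outcome enter the whole-study by-visit ALC summaries and median plot at odd visits reached under Version 5, with no safeguard. Any resulting bias in the median is downward. The probable location is around Years 4-6, which depends on when 12-weekly testing for all returned.

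The size is conditional on p, σ, the version mix and the stability of testing class, none of which the documents give. It ranges from negligible where few Version 5 subjects contribute to large where they dominate. The change is worth making because it is cheap and the curve bears on the primary objective. It does not call the adverse event, shift or worst-value results into question.

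**What to change.** In SAP 6.5.6, and in SAP 6.5.4 for lymphocytes and for WBC with differential, present the Year 4-8 by-visit summaries and the median plot at the 24-weekly visits only (Weeks 168, 192, ..., 384). State that the windows keep their present half-width of about 6 weeks. If the midpoint rule of SAP 6.3.8 were reapplied to visits 24 weeks apart, the windows would widen to about 12 weeks either side and could absorb the odd-visit values.

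If odd visits are to be shown, exclude values collected while the subject was under Version 5, and unscheduled repeats under Versions 3-4. Footnote the schedule change and give the number of values by protocol version at each visit.

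The first option costs plotted timepoints, including some unselected values. The second needs a protocol-version flag per subject visit, which the documents do not show to exist. Neither needs new data.
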